## 6.2 Usage of Concurrent/Concomitant Medications

No formal drug interaction studies have been conducted with trametinib. There is a low likelihood of drug-drug interactions with trametinib.

Trametinib has a high passive permeability and is eliminated primary via deacetylation, which is mediated by hydrolytic enzymes that are generally not associated with drug interaction risks. It is also not an in vitro substrate for human Pgp, BCRP, MRP2 and MATE1. In addition, due to trametinib's low efficacious dose and low systemic maximal concentration (22 ng/mL or 0.04  $\mu$ M) relative to its in vitro CYP inhibition/induction potency. Therefore, the risk of a drug-drug interaction by trametinib as both perpetrator or as a victim is low. See also Section 4.3.6 for detailed discussion.

## 6.3 Dietary Restrictions

Trametinib should be taken with a full glass of water, without food, at least 1 hour before or 2 hours after a meal. If a dose of trametinib is missed, the dose can be taken if it is more than 12 hours until the next scheduled dose.

Administration of a single dose of trametinib with a high-fat, high-calorie meal resulted in a 70%, 24%, and 10% decrease in Cmax, AUC(0-t), and AUC(0- $\infty$ ), respectively compared to fasted conditions.

## 6.4 Prohibited Medications

All treatments that the investigator considers necessary for a subject's welfare may be administered at the discretion of the investigator in keeping with the community standards of medical care. Palliative and supportive care is permitted during the course of the trial for underlying medical conditions and management of symptoms. Surgery or radiotherapy for tumor controls not permitted during the study; however, radiotherapy or procedures for symptom management is allowed.

Subjects are prohibited from receiving antineoplastic systemic chemotherapy or biological therapy not specified in this protocol.

Bisphosphonates or denosumab are allowed for patients with bone metastases.

Growth factor support may be considered for patients with neutropenia after discussion with the study PI.

Avoid concurrent use of strong CYP3A inhibitors during treatment.

Medications known to produce QT prolongation should be avoided during treatment of patients with and trametinib. See <http://crediblemeds.org/> for the most up-to-date reference lists of QT-prolonging medications. Please note that the lists contain common supportive medications, such as anti-emetics (ondansetron [and other 5HT3 antagonists], metoclopramide, hydroxyzine), antibiotics (azithromycin, ciprofloxacin, metronidazole) and anti-depressants (escitalopram).

Medications to consider for nausea that are not associated with QT prolongation include:

- Steroids (dexamethasone, methylprednisolone)
- Benzodiazepines
- Aprepitant
- Select anticholinergic agents (scopolamine)
- Trimethobenzamide
- Cannabinoids

## **7 Reporting and Documentation of Results**

### **7.1 Evaluation of Efficacy (or Activity)**

#### **7.1.1 Antitumor Effect – Solid Tumors**

Response and progression in this study will be evaluated using the new international criteria proposed by the Response Evaluation Criteria in Solid Tumors ([RECIST](#)) Committee [JNCI 92(3):205-216, 2000]. Changes in only the largest diameter (unidimensional measurement) of the tumor lesions are used in the RECIST v1.1 criteria.

#### **Definitions**

##### **Evaluable for toxicity**

All patients will be evaluable for toxicity from the time of their first treatment with the study drug.

##### **Evaluable for objective response**

Only those patients who have measurable disease present at baseline, have received at least one cycle of therapy, and have had their disease re-evaluated will be considered evaluable for response. These patients will have their response classified according to the definitions stated below. (Note: Patients who exhibit objective disease progression prior to the end of Cycle 1 will also be considered evaluable.)

#### **7.1.1.1 Disease Parameters**

##### **Measurable disease**

Measurable disease is defined as lesions (or tumors) that can be accurately measured in at least one dimension (longest diameter to be recorded) with a minimum size of 10mm by CT scan (irrespective of scanner type) and MRI (no less than double the slice thickness and a minimum of 10mm), 10mm caliper measurement by clinical exam (when superficial), and/or 20mm by chest X-ray (if clearly defined and surrounded by aerated lung).

All tumor measurements will be recorded in millimeters or decimal fractions of centimeters. Previously irradiated lesions are considered non-measurable except in cases of documented progression of the lesion since the completion of radiation therapy.

##### **Target lesions**

All measurable lesions up to a maximum of 5 lesions total (and a maximum of two lesions per organ) representative of all involved organs should be identified as target lesions and recorded and measured at baseline. Target lesions will be selected on the basis of their size (lesions with the longest diameter) and their suitability for accurate repeated measurements (either by imaging techniques or clinically). A sum of the longest diameter (LD) for all target lesions will be

calculated and reported as the baseline sum LD. The baseline sum LD will be used as reference by which to characterize the objective tumor response.

### **Non-target lesions**

All other lesions (or sites of disease) including any measurable lesions over and above the 5 target lesions should be identified as non-target lesions and should also be recorded at baseline. It is possible to record multiple non-target lesions involving the same organ as a single item on the case record form (e.g. “multiple enlarged pelvic lymph nodes” or “multiple liver metastases”). Bone lesions may be measurable if  $\geq 1$  cm on MRI. Measurements of these lesions are not required, but the presence or absence of each will be noted throughout follow-up.

### **Non-measurable disease (Tumor Markers)**

Non-measurable disease is all other lesions (or sites of disease), including small lesions (longest diameter  $< 20$  mm with conventional techniques or  $< 10$  mm using spiral CT scan). Leptomeningeal disease, ascites, pleural or pericardial effusion, inflammatory breast disease, lymphangitic involvement of skin or lung, abdominal masses/abdominal organomegaly identified by physical exam that is not measurable by reproducible imaging techniques are all non-measurable. (e.g., PSA, CA-125, CA19-9, CEA)

#### **7.1.1.2 Methods for Evaluation of Measurable Disease**

All measurements will be taken and recorded in metric notation using a ruler or calipers. All baseline evaluations will be performed as closely as possible to the beginning of treatment and never more than 28 days before the beginning of the treatment.

The same method of assessment and the same technique will be used to characterize each identified and reported lesion at baseline and during follow-up. Imaging-based evaluation is preferred to evaluation by clinical examination when both methods have been used to assess the antitumor effect of a treatment.

### **Conventional CT and MRI**

Spiral CT scans should be performed using a 5 mm contiguous reconstruction algorithm.

#### **7.1.1.3 Response Criteria**

##### **Evaluation of Target Lesions**

###### **Complete Response (CR)**

Disappearance of all target lesions, determined by two separate observations conducted not less than 4 weeks apart. Any pathological lymph nodes (whether target or non-target) must have reduction in short axis to  $< 10$  mm (the sum may not be “0” if there are target nodes). There can be no appearance of new lesions.

###### **Partial Response (PR)**

At least a 30% decrease in the sum of the longest diameter (LD) of target lesions, taking as reference the baseline sum LD. There can be no appearance of new lesions.

###### **Progressive Disease (PD)**

At least a 20% increase in the sum of the SLD of target lesions, taking as reference the smallest sum SLD recorded since the treatment started and minimum 5 mm increase over the nadir, or the appearance of one or more new lesions.

**Stable Disease (SD)**

Neither sufficient shrinkage to qualify for PR nor sufficient increase to qualify for PD, taking as reference the smallest sum LD since the treatment started.

**Evaluation of Non-Target Lesions**

**Complete Response (CR)**

Disappearance of all non-target lesions and normalization of tumor marker level. All lymph nodes must be non-pathological in size (< 10 mm short axis).

**Incomplete Response/Stable Disease (SD)**

Persistence of one or more non-target lesion(s) and/or maintenance of tumor marker level above the normal limits.

**Progressive Disease (PD)**

Appearance of one or more new lesions and/or unequivocal progression of existing non-target lesions.

**Evaluation of Best Overall Response**

The best overall response is the best response recorded from the start of the treatment until disease progression/recurrence (taking as reference for progressive disease the smallest measurements recorded since the treatment started). The patient's best response assignment will depend on the achievement of both measurement and confirmation criteria.

**Table 7.1 Response Criteria**

| Target Lesions | Non-Target Lesions | New Lesions | Overall Response | Best Response for this Category Also Requires |
|-----------------------|---------------------------|--------------------|-------------------------|--|
|-----------------------|---------------------------|--------------------|-------------------------|--|

|     |                   |           |    |  |
|-----|-------------------|-----------|----|--|
| CR  | CR                | No        | CR | > 4 weeks confirmation                           |
| CR  | Non-CR/
Non-PD | No        | PR | > 4 weeks confirmation                           |
| PR  | Non-PD            | No        | PR |  |
| SD  | Non-PD            | No        | SD | documented at least once > 4 weeks from baseline |
| PD  | Any               | Yes or No | PD | no prior SD, PR or CR                            |
| Any | PD*               | Yes or No | PD |  |
| Any | Any               | Yes       | PD |  |

\* In exceptional circumstances, unequivocal progression in non-target lesions may be accepted as disease progression

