## 2.4 Endpoints

### 2.4.1 Primary Endpoints

- Objective Response Rate (ORR) according to RECIST Version 1.1 criteria as determined by investigator assessment. The ORR is defined as the best overall response recorded from the start of the treatment until disease progression or recurrence from the start of treatment.

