### 2.4.2 Secondary Endpoints

- Efficacy: DR, DCR, PFS, and OS according to RECIST Version 1.1 criteria as determined by investigator assessment.
  - The DR for CR and PR will be measured from the date that the best response is first recorded until the date that PD is documented. For patients who continue treatment post progression, the date of PD documentation will be used for analysis.
  - DCR will be defined as the percentage of patients who have achieved CR, PR, or SD for at least 12 weeks.
  - PFS will be calculated as 1+ the number of days from the first dose of study drugs to documented radiographic progression or death due to any cause over a period of 1 year. For patients who continue treatment post-progression, the date of radiographic progression will be used for PFS analysis.
  - OS will be calculated as 1+ the number of days from the first dose of study drugs to death due to any cause over a period of 1 year.
- Safety and tolerability:
  - All treatment-emergent AEs
  - Treatment-emergent AEs by CTCAE grade
  - Grade 3 or greater treatment-emergent AEs
  - Treatment-related, treatment-emergent AEs
  - Dose-limiting toxicity AEs
  - Serious treatment-emergent AEs
  - Treatment-emergent AEs with an outcome of death
  - Treatment-emergent AEs leading to discontinuation of trametinib.
  - Treatment-emergent AEs resulting in interruption or reduction or delay of trametinib.

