### 8.3.3

## Secondary Analysis (or Analysis of Secondary Endpoints)

### Definition and analytical plan for secondary efficacy endpoints:

**(a) Duration of response (DR):** The DR for CR and PR will be measured from the date that the best response is first recorded until the date that PD is documented over the period of 1 year. For patients who continue treatment post progression, the date of PD documentation will be used for analysis. The DR will be summarized using descriptive statistics (N, mean, standard deviation, minimum, and maximum).

**(b) Disease control rate (DCR):** DCR will be defined as the percentage of patients who have achieved CR, PR, or SD for at least 12 weeks. The DCR will be summarized using descriptive statistics (N, mean, standard deviation, minimum, and maximum).

**(c) Progression-free Survival (PFS):** PFS will be calculated as 1+ the number of days from the first dose of study drugs to documented radiographic progression or death due to any cause over a period of 1 year. For patients who continue treatment post-progression, the date of radiographic progression will be used for PFS analysis. The Kaplan-Meier analysis will be used to calculate the median PFS with 95% confidence interval.

**(d) Overall Survival (OS):** OS will be calculated as 1+ the number of days from the first dose of study drugs to death due to any cause over a period of 1 year. The Kaplan-Meier analysis will be used to calculate the median OS with 95% confidence interval.

**(3) Definition and analytical plan for safety and tolerability endpoints:** The safety population will consist of all subjects who receive any amount of study treatment. Safety will be assessed by evaluation of AEs. All safety analyses will be performed using the safety population. Adverse event terms recorded on the CRFs will be mapped to preferred terms using the Medical Dictionary for Regulatory Activities (MedDRA). Seriousness, severity grade and relationship to study treatment will be assessed by the investigator. Severity grade will be defined by the National Cancer Institute (NCI) CTCAE v4.03. Listings of AEs will be provided.

Separate tables will present the following by dose group and study phase:

- All treatment-emergent AEs
- Treatment-emergent AEs by CTCAE grade
- Grade 3 or greater treatment-emergent AEs
- Treatment-related, treatment-emergent AEs
- Dose-limiting toxicity AEs
- Serious treatment-emergent AEs
- Treatment-emergent AEs with an outcome of death

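### The Table 7.1 footnote makes PD on non-target lesions discretionary, in conflict with the unconditional definition in Section 7.1.1.3

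*Combined protocol and SAP*

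**What the plan says.** Section 7.1.1.3, under the evaluation of non-target lesions, defines progressive disease as: "Appearance of one or more new lesions and/or unequivocal progression of existing non-target lesions". No condition is attached.

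Table 7.1 has a row for any target status with non-target PD, with or without new lesions. Its overall response is PD, but the non-target entry carries an asterisk, and the footnote reads: "In exceptional circumstances, unequivocal progression in non-target lesions may be accepted as disease progression".

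The endpoints depend on this call:

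- The primary endpoint (Section 2.4.1) is "Objective Response Rate (ORR) according to RECIST Version 1.1 criteria as determined by investigator assessment".
- Section 7.1.1.3 closes the response window at progression: "The best overall response is the best response recorded from the start of the treatment until disease progression/recurrence".
- PFS (Section 8.3.3(c)): "PFS will be calculated as 1+ the number of days from the first dose of study drugs to documented radiographic progression or death". Target and non-target progression are not distinguished.
- DCR (Section 2.4.2): "DCR will be defined as the percentage of patients who have achieved CR, PR, or SD for at least 12 weeks".
- Duration of response (Sections 2.4.2 and 7.1.1.3) ends at documented PD.

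The Abstract and Sections 2.4.1 and 2.4.2 name RECIST 1.1. Section 7.1.1 also names v1.1 but gives "JNCI 92(3):205-216, 2000" as the source of the criteria.

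**The concern.** A rule cannot be both unconditional and something that may be granted in undefined special cases. Two investigators reading the same scan, one from the definition and one from the footnote, could reach different decisions on whether PD has occurred and on which date. The plan does not say what counts as exceptional or which text prevails.

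This matters more here than in a controlled, blinded trial. Sections 8.1.1 and 8.1.2 describe a single-arm, open-label study, and Section 2.4 names the investigator as assessor. ORR is tested against a fixed 10% (Section 8.2.1), so no control arm absorbs a shift in scoring. The discretion also works in one direction: relative to the definition, it can remove or delay a PD but never add one.

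**Working it through.** The plan gives no figure on this point, so the main check is a comparison of the texts. The arithmetic that follows is illustrative.

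**1. Which scans are affected.** Table 7.1 gives PD by three routes: target PD, non-target PD (asterisked) and a new lesion. The first and third do not depend on the footnote. It therefore matters only when the targets have not progressed, there is no new lesion, and existing non-target disease has unequivocally progressed.

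**2. What the table gives such a scan if PD is withheld.** The SD row and the row from target PR to overall PR both require non-target Non-PD. The row from target CR to overall PR requires Non-CR/Non-PD. The CR row requires non-target CR. No row remains, so on the restrictive reading the scan has no defined overall response.

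**3. Direction, endpoint by endpoint, against the Section 7.1.1.3 definition.**

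- *PFS:* every withheld PD moves the event to a later date, unless death occurs first. This is the most exposed endpoint.
- *DCR:* changes only if the withheld PD falls before 12 weeks of disease control and no earlier CR or PR already counts.
- *Duration of response:* changes only in responders whose response ends in non-target progression alone.
- *ORR:* changes only if the first qualifying target response comes at or after the non-target progression. A response recorded before it counts either way.

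**4. Illustration for PFS.** The 8-week scan interval is from the Abstract. The other inputs are assumptions found nowhere in the documents: exponential progression with a 12-week median, a share q of 10% to 20% of progressions that are non-target only and dated one scan late, and no death in the added interval.

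- S(t) = 2^(−t/12), so S(8) = 0.630 and S(16) = 0.397.
- A patient who progresses between weeks 8 and 16 and is dated one scan late counts as progression-free beyond the week-16 scan. The scored proportion is therefore S(16) + q × [S(8) − S(16)].
- q = 0: 0.397, or 40%.
- q = 0.10: 0.397 + 0.10 × 0.233 = 0.420, or 42%.
- q = 0.20: 0.397 + 0.20 × 0.233 = 0.443, or 44%.

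**5. ORR and type I error.** The documents state no final cut-off. With 27 patients and at least 2 responses required in the first 15, the smallest cut-off that keeps the one-sided exact error at or below 5% under a 10% ORR is 6 responses. The error is Σ over x = 2 to 15 of P(X1 = x) × P(X2 ≥ 6 − x), with X1 ~ Bin(15, p) and X2 ~ Bin(12, p). At p = 0.10 this is 4.5%. With 24 patients and the same cut-off it is 2.7%. If no patient becomes a responder through the footnote, p stays at 0.10 and neither figure moves.

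**The case against.** The best defence is that the plan already points to PD. The definition says so, the row says so, and RECIST 1.1 is the declared standard. The footnote does not say that non-target progression is accepted *only* in exceptional circumstances. It can be read as a caution against calling PD lightly on non-target disease alone. Much of this stands, and it is why the point is conditional. It does not remove the conflict: the footnote is attached to the very entry that produces PD, it is the printed rule from which sites would score, and the section that names v1.1 cites a publication from 2000. The text of RECIST 1.1 is not in the documents, so they cannot settle the matter by reference to it.

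Three stronger readings are tempting, and the documents do not support them.

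- *A reader might infer that the scan would be scored SD or even PR.* Those rows require a non-target status other than PD. Reaching them means relabelling the lesions as not progressed, which no text authorises and the definition contradicts.
- *A reader might infer that ORR, DCR and PFS are biased upward.* That follows only if investigators use the footnote to withhold PD, and nothing shows that they will.
- *A reader might infer that the type I error is materially inflated.* The formula above gives 9.4% at a scored rate of 12% and 15.1% at 13.7% (10% plus one patient in 27, or 3.7 points). Those rates are assumed and the cut-off is derived. They also imply that 2/12 = 17% or 3.7/13.7 = 27% of scored responders first responded in their targets at or after unequivocal non-target growth. The documents give no basis for shares of that size.

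**Conclusion.** The point holds as a conflict between an operative scoring rule and its footnote. The footnote turns an unconditional PD into a discretionary one, leaves the exception undefined, and leaves the scan without a row if PD is withheld. Measured against the definition, any effect on PFS, DCR, duration of response or ORR is zero or upward.

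The size cannot be derived from the documents. Under the stated assumptions, PFS beyond the week-16 scan moves by about 2 to 5 percentage points (0.397 to between 0.420 and 0.443). No DCR or duration-of-response effect was calculated. ORR should be affected rarely and possibly not at all, so this is not evidence that the primary test is invalid. It is a modest defect, worth correcting because the same investigator makes the call and assesses the endpoints without a comparator.

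**What to change.** Delete the Table 7.1 footnote and its asterisk, or replace the footnote with: *Unequivocal progression of non-target lesions is PD whatever the target-lesion response.* State that PFS and duration of response take their progression date from that scan. The table then agrees with the Section 7.1.1.3 definition and with the outcome of its own row.

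The cost is one line of protocol wording and no new assessments. The downside is that PFS, DCR and ORR may look slightly less favourable than under a lenient use of the footnote.

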**Duration of Response**

**Duration of overall response**

The duration of overall response is measured from the time measurement criteria are met for CR or PR (whichever is first recorded) until the first date that recurrent or progressive disease is objectively documented (taking as reference for progressive disease the smallest measurements recorded since the treatment started).

The duration of overall CR is measured from the time measurement criteria are first met for CR until the first date that recurrent disease is objectively documented.

### Duration of stable disease

Stable disease is measured from the start of the treatment until the criteria for progression are met, taking as reference the smallest measurements recorded since the treatment started.

### Progression-Free Survival

Progression-free survival (PFS) is defined as the duration of time from start of treatment to time of progression.

## **7.2 Evaluation of Safety**

Analyses will be performed for all patients having received at least one dose of study drug. The study will use the [CTCAE v4.03](#) for reporting of non-hematologic adverse events and modified criteria for hematologic adverse events, [REDACTED]

For multicenter studies, the Principal Investigator at the UCSF Coordinating Center will hold the role of Study Chair. The Study Chair is responsible for the overall conduct of the study and for monitoring its safety and progress at all participating sites.

